- Persons who respond to recruitment materials or face-to-face meetings will be asked for consent to be screened for eligibility. After participants are deemed eligible they will be scheduled for a baseline assessment, and they will be randomly assigned to the dance treatment or to the health education control group using Study360 software.
- Individuals who are not eligible for the study will be thanked for their time.
- Testings will take place at Baseline, 4-months (posttesting), and 8-months (end of maintenance intervention) at the Clinical Research Center (CRC), participant's home, Senior Center, and our Lab Building at UIC; and the intervention will take place at various senior centers, community centers, parks, etc.. Data collection research staff will not be told to which experimental group (BAILAMOS or control) participants are in. Participants will be offered a ride from FlashCab taxi service (using an established contract of the PI with FlashCab), which will transport participants from their homes to the UIC CRC and vice versa.
- At the testing sessions a staff member will explain the study and read the Informed Consent form aloud to the participant. After participants agree to participate, they will sign the Informed Consent. All measures are available in Spanish or English.

- All participants will then have their heart rate, blood pressure, height and weight taken. Participants will then complete interviewer-administered questionnaires and tests of physical functioning (balance, mobility, and strength).
- Accelerometers. At testing they will be given an accelerometer to wear for one week and return to study staff. At the last class participants will be given an accelerometer to wear for one week. Participants will return for assessment and to return accelerometers.
- Intervention. The BAILAMOS© program. BAILAMOS© includes a 4-month, twice-weekly dance program. The PI and a professional dance instructor co-developed an extensive BAILAMOS© Dance Manual and class-by-class schedule. A 4-month maintenance intervention including the twice-weekly dance program will be completed.

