- Sedentary older Latinos randomly assigned to the health education control group will participate in classes developed for older adults and offered by the University of Illinois Extension for the past 10 years. All classes are conducted in Spanish by extension staff using Spanish-language materials. The curriculum covers topics such as heart disease, diabetes, cancer, stress, asthma, osteoporosis, immunizations, home safety, and sexual health. Classes will meet one day per week for two hours, to provide equitable social contact as the treatment group.
- If participants are put into the health education program, they will be offered a short, 4-session dance program during the additional 4-month period, consisting of one class for each of the four styles of dance taught in the larger BAILAMOS© dance program.
- For the dance group and the health education group, separate lotteries will occur during the initial 4-month program and the follow-up 4-month maintenance program. All participants who meet criteria of having attended 75% of classes over each 4-week period are eligible for the lottery. One lottery will happen every four weeks (four lotteries total for the initial 4-month program and four lotteries for the follow-up 4-month maintenance program), and two participants from the dance group will win \$50 and two participants from the health education group will win \$50 for each lottery. All participants who are eligible will have an equal chance of winning, and the odds of winning are dependent upon the number of participants who meet lottery eligibility criteria (for example, if 10 participants are eligible, you have a 1/10 or 10% chance of winning). For each lottery, if you are eligible, your name will be put into a hat; the winner will be randomly drawn from the hat; your name will not be linked to research data; and the names will be destroyed immediately after the lottery occurs.
- At 4-months post-intervention, and at 8-months, testing will occur. Questionnaires and tests will be administered in the same order as baseline and 4-month testing.
- After the PRE-intervention testing (baseline/month 0) a \$10 cash gift will be provided, and participants will be asked to wear an accelerometer for 7 days. When that accelerometer is returned, participants will receive another \$10 cash gift.

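### Section 4.e, as written, randomises at eligibility and scheduling, before trial consent and baseline measurement; if the arm is disclosed that early, consent and baseline data can depend on it

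*Combined protocol and SAP*

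**What the plan says.** Section 4.e describes the route into the trial in a list. People who respond to recruitment "will be asked for consent to be screened for eligibility". The same item continues: "After participants are deemed eligible they will be scheduled for a baseline assessment, and they will be randomly assigned to the dance treatment", with health education as the alternative and Study360 making the assignment. A later item turns to the testing visits: "At the testing sessions a staff member will explain the study and read the Informed Consent form aloud to the participant". It goes on: "After participants agree to participate, they will sign the Informed Consent". The measurements come next: "All participants will then have their heart rate, blood pressure, height and weight taken", and "Participants will then complete interviewer-administered questionnaires and tests of physical functioning (balance, mobility, and strength"). The baseline accelerometer week follows that visit: "After the PRE-intervention testing (baseline/month 0) a \$10 cash gift will be provided, and participants will be asked to wear an accelerometer for 7 days".

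Section 4.d gives a shorter account in which eligibility leads to scheduling of the baseline visit; randomisation is not mentioned there. On masking, section 4.e says only that data collection staff are not told the group. Section 4.b makes acceptance of either arm an inclusion criterion.

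**The concern.** The arms are dance classes and health education classes, so a participant who has been told the assignment cannot be masked to it. If that happens before consent and baseline, two things can go wrong.

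- **Selective loss.** Someone who hoped to dance may decline, or not attend, on learning of assignment to health education. That person has been randomised but leaves neither baseline nor outcome data. The mixed model and the dropout check in section 4.f have nothing to work with. The plan does not say whether such a person counts towards the 166 per arm or belongs to the analysis set.
- **Coloured baselines.** Lifestyle PA is partly self-reported, self-efficacy is a matter of stated confidence, and the questionnaires are given by interview. Knowing the arm can change these answers, and can change how active a person is during the accelerometer week.

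Section 4.f uses the baselines twice: the effect is the Group x Time interaction, and baseline variables that differ between arms become covariates. A baseline influenced by the arm would therefore reach both the estimate and its adjustment.

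**Working it through.** The question is one of order, so the first step is to set the statements side by side.

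| Step | Where | Timing given |
|---|---|---|
| Agreement to be screened | 4.e | Before eligibility is settled |
| Scheduling of baseline visit | 4.d and 4.e | Once eligible |
| Randomisation in Study360 | 4.e only | Once eligible, in the same sentence as scheduling |
| Study explained, consent signed | 4.e | At the testing session |
| Baseline questionnaires and function tests | 4.e | At the testing session, after consent |
| Baseline accelerometer | 4.e | 7 days, after the baseline visit |
| Disclosure of arm to participant | Nowhere | Not stated |

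The description of baseline as pre-intervention testing fixes it relative to the classes, not relative to randomisation. The masking sentence sits with the list of all three testing occasions, baseline included. That fits an assignment which already exists at baseline, but does not prove it.

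**What each mechanism would do to the planned contrast.** Write D for the dance mean and H for the health education mean, at months 0 and 4. The simple form of the Group x Time contrast is

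C = (D4 − D0) − (H4 − H0).

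- Selective refusal that shifts the PA *level* of those remaining in H by b at both times changes C by −(b − b) = 0. A stable level difference cancels.
- Selective refusal related to later *change*, so that those remaining in H change by s more than the full arm would have, alters C by −s.
- A shift r confined to the baseline reports or baseline accelerometer week alters C by −r if it occurs in D and by +r if it occurs in H. It passes through in full.

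**How large could b be?** The documents give no rates, so this is purely an assumption. If a share f of one arm declines, and decliners differ from the full-arm mean by d SD, the mean of those remaining shifts by b = f/(1 − f) × d in absolute size.

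- f = 0.05, d = 0.25: 0.05/0.95 × 0.25 = 0.013 SD
- f = 0.10, d = 0.50: 0.10/0.90 × 0.50 = 0.056 SD
- f = 0.20, d = 0.50: 0.20/0.80 × 0.50 = 0.125 SD

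These are imbalances in level, which the first bullet above shows largely drop out of the planned test. The quantities that matter, s and r, cannot be bounded from the documents.

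The plan has no figure of its own to reproduce here. The 166 per arm in section 3 comes without a significance level, power, target effect or dropout rate, and the point does not depend on it.

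**The case against.** The strongest reply is that the order is inferred. The joining word in the randomisation sentence does not strictly exclude assignment after the baseline visit, and the list in section 4.e is not chronological throughout. It deals with ineligible people after randomisation, names the month 4 and month 8 testing before consent, and mentions the accelerometer handed out at the last class before describing the classes. This stands, and limits the claim to what the text allows. It does not remove the point: the plain reading puts assignment at eligibility, and no other sentence corrects it.

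Second, early randomisation does harm only if the participant, or staff dealing with the participant, know the arm before baseline. No sentence says so. This also stands, and makes the concern conditional.

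Third, there are safeguards. People unwilling to accept either arm should be screened out. Control participants are offered a four-session dance program and have their own lotteries, which lowers the incentive to refuse. Data collectors are masked. These reduce refusal and interviewer bias; they do not protect a participant's own answers or behaviour in the accelerometer week once the arm is known.

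Fourth, the consent pages are not in the available text, and section 4.h refers to an application describing Study360 in detail. Either may fix the order, so the gap can be claimed only for the text at hand.

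A reader might go further and infer that people were in fact told their arm before consenting, or that the results are biased by a known share of the effect the trial can detect. The documents support neither. Disclosure is not timed, and setting an assumed imbalance in PA level against a detectable effect would use the wrong quantity for a test of change.

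**Conclusion.** The concern holds in a conditional form. Followed as written, the protocol randomises people who have agreed only to screening, and leaves trial consent, baseline interviews and the baseline accelerometer week until afterwards, with no instruction to withhold the assignment. If the arm is disclosed in that interval, consent, attendance and baseline values can depend on it, and the Group x Time test and covariate selection would inherit the problem. The existing safeguards are partial.

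The size is unknown. It depends on when disclosure happens, how many decline by arm, and whether refusal relates to later change or knowledge of the arm shifts the baseline measures; the documents give none of these. Selective refusal that affects only a stable PA level would largely cancel. The gap should be closed because it is cheap to close and the plan offers no later means of detecting its effect.

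**What to change.** Replace the randomisation sentence in section 4.e with:

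> After signed consent, completion of the baseline visit and the end of the 7-day baseline accelerometer period (whether or not the device yields usable data), the participant is randomised in Study360 and then told the assignment.

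Tying release to the end of the wear period, rather than to return of the device, avoids barring people who do not return it.

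This is version 38, and its amendment text shows sites already in the maintenance phase, so new wording cannot change the order for participants already randomised. For them, report by arm how many were assigned before consent or before baseline, and how many of those never consented or had no baseline. Analyse the rest in the arm assigned. If baseline did come first in practice, the new sentence simply records that.

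The cost is one sentence, a release check in Study360 and a short table in the report. The downside is that participants learn their assignment about a week later.

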- 1. Our Lady of Mount Carmel
- 2. West Town Satellite Senior Center
- 3. Pilsen Satellite Senior Center (Alivio Medical Center)
- 4. Kelvyn Park Satellite Senior Center
- 5. Villa Guadalupe Senior Services INC
- 6. Southwest Center
- 7. St. Agnes of Bohemia
- 8. West Suburban Senior Services
- 9. Catholic Charities of Archdiocese of Chicago, St Mary of Celle
- 10. Northwest Copernicus Regional Senior Center
- 11. Holy Cross Immaculate Heart of May Church
- 12. Mile Square Health Center—Recruitment ONLY
- 13. Dance Academy of Salsa

f. Statistical Methods

Aim 1. Hypothesis: Lifestyle PA (self-reported and accelerometer-assessed) will be significantly higher in the BAILAMOS© group at 4 and 8 months compared to the control group.

The proposed study uses a between-groups design with two groups and individual covariates. Initially, descriptive statistics will be obtained (e.g., for continuous variables we will examine means and standard deviations) and we will screen for wild codes (e.g., extreme values as the result of typos in data entry).

Using t-tests and chi-square tests, we will examine all baseline outcomes and covariates to determine whether randomization has produced equivalent groups. Variables exhibiting differences will be added as covariates to analyses. Transformations to achieve normality will be applied as needed; and residuals from analysis will be examined to detect multivariate outliers. Data will be examined for differential dropout but dropout is expected to be missing at random (MAR) and will thus not be imputed unless necessary.

Analysis will be carried out using standard mixed model analysis of variance and covariance using the SAS program (i.e., PROC MIXED), controlling for antecedent factors measured at

baseline including demographics, body composition, acculturation, and health status. For Aim 1 the Group x Time interaction term will test whether there is greater improvement in self-reported and accelerometer-assessed lifestyle PA at 4 and 8 months in the treatment group compared to the control group.

Aim 2. Hypothesis 2a: Self-efficacy for PA, Balance, and Gait will be significantly higher in the BAILAMOS© group at 4 and 8 months compared to the control group.

The same analysis strategy in Aim 1 will be applied for Aim 2, Hypothesis 2a. The Group x Time interaction term will test whether there is greater improvement in self-efficacy at 4 and 8 months in the treatment group compared to the control group.

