Aim 2. Hypothesis 2a1: Self-efficacy for PA, Balance, and Gait will mediate the effect of the BAILAMOS© program on lifestyle PA and health outcomes.

In connection with Aim 2, Hypothesis 2a, we will conduct mediation analysis following testing procedures recommended by MacKinnon. We will examine whether self-efficacy is a necessary intervening variable to produce the PA and health outcome differences. We will use methods provided in the M-Plus statistical package, which offers special facilities for estimating standard errors of mediation terms.

Aim 2. Hypothesis 2b: Physical function, cognitive function, and self-reported functional limitations and disability scores will be significantly better in the BAILAMOS© group at 4 and 8 months compared to the control group.

Analysis will be the same as Aims 1 and 2. The Group x Time interaction term will test whether there is greater improvement in physical function, cognitive function, and self-reported functional limitations and disability scores at 4 and 8 months in the treatment group compared to the control group.

g. Safety Monitoring and Assessment

Risks:

The risk level of the intervention is minimal. For the proposed study there is the potential that undocumented Latinos will want to participate and will be concerned about anonymity and confidentiality in participating.

There is a small possibility that the older adults could injure themselves during the testing or the dance program.

Possible risks associated with physical injury that could occur during the dance intervention include those that one would experience with any physical activity, including (1) strains, sprains, muscle soreness, aggravation of arthritic conditions, etc. (2) slipping/tripping/falling; (3) bumping into another participant; (4) a very slim chance that cardiac irregularities can occur. This is very rare and the benefits of exercise are known to outweigh the risks. Serious physical injury or severe pain is considered unlikely. In our pilot test of the BAILAMOS© dance program, we had 12 participants, 9 of whom completed the 12 week program that took place two times per week. We experienced no serious injuries or falls.

The following provides steps that we will take to (1) address the potential for risks, and (2) handle injuries should they occur.

- 1) Addressing the potential for risks

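### Section 4.f picks extra covariates by baseline significance tests and does not name the outcome's own baseline; the planned Group x Time test is valid, but usually less precise than prespecified baseline adjustment.

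*Combined protocol and SAP*

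**What the plan says.** All of this is in Section 4.f, Statistical Methods. The screen: "Using t-tests and chi-square tests, we will examine all baseline outcomes and covariates to determine whether randomization has produced equivalent groups". The rule that follows: "Variables exhibiting differences will be added as covariates to analyses". No test level is given, and nothing says whether an added variable enters as a main effect or together with Time.

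The model is a mixed model in SAS that controls for baseline factors, introduced by the word including: "demographics, body composition, acculturation, and health status". The outcome's own baseline is not named there, although it is among the variables screened.

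The Aim 1 test of treatment, which covers both follow-up visits, is worded thus: "the Group x Time interaction term will test whether there is greater improvement in self-reported and accelerometer-assessed lifestyle PA". The plan carries this to the other outcomes: "The same analysis strategy in Aim 1 will be applied for Aim 2, Hypothesis 2a" and, for Hypothesis 2b, "Analysis will be the same as Aims 1 and 2". Section 4.a sets testing at months 0, 4 and 8. Whether month 0 is a response in the model is not stated, but a test of improvement implies it.

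**The concern.** Under randomisation a baseline difference between arms is a chance event. A significance test for it does not show whether the variable predicts the outcome, and prediction is what makes adjustment worthwhile. The rule therefore selects covariates on the wrong criterion, and does so only after the arms have been compared.

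The variable most likely to predict a follow-up score is the same score at baseline. The plan uses it through the change contrast, or as a covariate if chance flags it. What is at stake is precision, and a model settled in advance, for every between-group test in Aims 1, 2a and 2b.

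**Working it through.** **Inputs.** From the documents: 166 per arm (Section 3) and visits at months 0, 4 and 8 (Section 4.a). No alpha, power, effect size, SD or correlation accompanies the 166, so it cannot be reproduced and is taken as given. Assumed: two-sided 0.05, complete data unless stated, baseline SD s0, follow-up SD s1, and correlation ρ between baseline and follow-up of 0.3, 0.5, 0.7 or 0.8.

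**Step 1: the planned contrast.** With month 0 as a response and free group means, Group x Time at one follow-up visit is the difference in mean change. Its variance per participant is Vc = s0² + s1² − 2ρ·s0·s1. It is unbiased under randomisation. In simulation (equal SDs, 166 per arm, ρ = 0.3, 0.5, 0.7) it rejected 5.1%, 5.2% and 5.0% of null trials. With a true difference of 0.30 SD its mean estimate was 0.300, 0.301 and 0.300.

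**Step 2: baseline adjustment.** The variance is Va = s1²(1 − ρ²), so Vc − Va = (s0 − ρ·s1)². This is never negative, and it is zero only when s0 = ρ·s1.

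**Step 3: size.** With equal SDs, Va/Vc = (1 + ρ)/2, so the variance cut is (1 − ρ)/2. If the change contrast has 80% power, the adjusted contrast has Φ(2.80/√((1 + ρ)/2) − 1.96). At ρ = 0.5 that is Φ(2.80/0.866 − 1.96) = Φ(1.27) = 0.90. The number per arm that would match the change contrast with 166 is 166(1 + ρ)/2, rounded up.

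With unequal SDs the cut is 1 − Va/Vc. For s1 = 1.25·s0 and ρ = 0.5 (s0 = 1), Vc = 1 + 1.5625 − 1.25 = 1.3125 and Va = 1.5625 × 0.75 = 1.1719, a cut of 11%.

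| ρ | Cut, s1 = s0 | 80% power becomes (s1 = s0) | Per arm to match 166 (s1 = s0) | Cut, s1 = 1.25·s0 | Cut, s1 = 0.8·s0 |
|---|---|---|---|---|---|
| 0.3 | 35% | 94% | 108 | 22% | 50% |
| 0.5 | 25% | 90% | 125 | 11% | 43% |
| 0.7 | 15% | 86% | 142 | 2% | 37% |
| 0.8 | 10% | 84% | 150 | 0% | 36% |

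**Step 4: the rule, with flagged variables as main effects.** A baseline covariate is constant over a participant's visits, so it cancels from within-person change. In a mixed model fitted to one simulated complete data set, the first follow-up Group x Time estimate was 0.2745 (SE 0.1033) with no covariate, with an age-like covariate, and with the outcome's baseline added as well.

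Under dropout it can move a little. With 23% to 25% dropout by month 8 (the pilot lost 3 of 12) and the outcome's baseline flagged at 0.05, adding that baseline and an age-like covariate moved the estimate by a median of 0.05 to 0.15 SE, at most 0.52 SE. The chance imbalance itself shifts the change contrast by an expected 2.338·√((1 − ρ)/2) SE, that is 1.38, 1.17, 0.91 and 0.74 SE. The rule largely leaves in place the imbalance it detects.

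**Step 5: the rule, with flagged variables entered with Time.** The contrast is then baseline-adjusted, but only when the outcome's baseline happens to be flagged, in about 5% of trials per outcome at an assumed 0.05 level. Simulated power at a true difference of 0.30 SD (equal SDs, ρ = 0.3, 0.5, 0.7) was:
- change contrast: 64%, 78%, 94%
- adjusting only after a flag: 65%, 79%, 94%
- always adjusting: 81%, 88%, 97%

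Adjusting only after a flag gave type I error of 4.1% to 4.6%.

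**The case against.** The strongest reply is that Group x Time on change is a valid and common analysis, and that the screening rule does not cause the loss of precision. The size of the loss also rests on SDs and correlations that the documents do not give. Section 4.b restricts exercise and dancing at entry, so a larger follow-up SD for physical activity is plausible, and that shrinks the gain. All of this stands. It limits the size of the point but does not remove it, because adjustment is never less precise in large samples.

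Four stronger readings are tempting but are not supported:
- **The rule inflates type I error or biases the result.** Overall error is about 5%. Among null trials with that outcome's baseline flagged, Group x Time does reject about 22% of the time at ρ = 0.3, falling to about 10% at ρ = 0.8 (equal SDs). That applies only if flagged variables enter as main effects; entered with Time, the rate is about 5%. It is regression to the mean in the change contrast, and the rule does not create it.
- **Every outcome loses precision.** The loss is zero when s0 = ρ·s1.
- **The outcome's baseline is excluded from adjustment.** The covariate list is open, so it is only not named.
- **Month 0 leaves the model once flagged, so that Group x Time compares only months 4 and 8.** The wording about improvement speaks against this.

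Timing is a further fair objection. Version 38 is dated June 2016, and the question added under Amendment #35 (Section 4.e) asks about the programme in the past tense, so follow-up may have been well advanced. A change to the main test would need to be dated and made without sight of results by arm.

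**Conclusion.** The point holds as one of efficiency and prespecification, not of bias or error rate. Significance tests at baseline are a poor way to choose covariates, and here they neither repair the imbalance dependably nor recover the lost precision. If flagged variables enter as main effects, the complete-data test does not change. If they enter with Time, the imbalance is corrected but the model depends on which variables chance flagged.

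The gain from adjustment ranges from substantial at low correlation to small at high correlation. It may vanish for an outcome whose spread grows after baseline, and is larger where the spread falls. The figures assume 166 per arm and complete data. The validity of Group x Time also needs a suitable covariance structure, which the plan does not state, and dropout that is missing at random.

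**What to change.** Delete the baseline significance tests and the rule that follows from them, and keep the baseline table as description. Fix one named covariate list drawn from the four stated domains. For every outcome in Aims 1, 2a and 2b, prespecify one of two models:

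- **(a)** Months 4 and 8 as responses, with the outcome's own baseline and baseline x Time as covariates. Replace Group x Time by a 2-df joint test that the group effect is zero at both visits. The replacement is needed because, with only these two responses, Group x Time would compare month 8 with month 4 and could not detect an effect equal at both.
- **(b)** Month 0 kept as a response, with its mean constrained equal across arms. Here the 2-df Group x Time test is already that joint test.

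Under either model, report the month-4 and month-8 contrasts. Multiplicity between the two months is a separate matter.

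The cost is rewording, since the variables are already collected, plus a few degrees of freedom. Option (a) drops participants who lack the outcome's baseline; option (b) keeps them. The gain may be small for some outcomes. The change should be dated and made before anyone examines unblinded outcome data.

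### Section 4.f tests efficacy by Group x Time but names no covariate-by-time term, so baseline covariates entered as main effects would leave that test in effect unadjusted

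*Combined protocol and SAP*

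**What the plan says.** All of this is in section 4.f (Statistical Methods), with testing at 0, 4 and 8 months and 166 participants per arm given in sections 3 and 4.a.

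- **Model.** The analysis is to be done "using standard mixed model analysis of variance and covariance using the SAS program (i.e., PROC MIXED), controlling for antecedent factors measured at" study entry. The factors listed are demographic variables, body composition, acculturation and health status. They are measured once and do not vary over visits.
- **Imbalance rule.** Baseline outcomes and covariates are compared between arms, and "Variables exhibiting differences will be added as covariates to analyses".
- **Tested term.** "For Aim 1 the Group x Time interaction term will test whether there is greater improvement in self-reported and accelerometer-assessed lifestyle PA", judged over both follow-up visits. For Hypothesis 2a, "The Group x Time interaction term will test whether there is greater improvement in self-efficacy at 4 and 8 months". For Hypothesis 2b, "Analysis will be the same as Aims 1 and 2", again with Group x Time as the test.
- **Missing outcomes.** Dropout is assumed missing at random and is not imputed unless necessary, so people with incomplete follow-up stay in the mixed model.

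The section does not say whether covariates enter as main effects only or also by visit, whether the month-0 outcome is a response or a covariate, or which covariance structure is used.

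**The concern.** The plan states two intentions that may not meet. It wants the arm comparison adjusted for baseline factors, including any that happen to be imbalanced. It also makes Group x Time, a contrast of within-person changes, the only test for Aim 1 and Hypotheses 2a and 2b. A time-constant covariate with one common slope shifts a person's outcome equally at every visit, so it has no bearing on that person's change.

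If the model is fitted that way, the imbalance rule acts on the group main effect, which is not the test, and leaves the tested term as it was. Two things are at stake: protection against a chance imbalance in a variable that predicts change, and the precision that covariates already collected could supply. The result could also be described as covariate-adjusted when the tested term is not.

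**Working it through.** The documents give no alpha, SD, effect size or power for these tests, so there is no figure of the plan's to reproduce. The point is algebraic; the numbers below illustrate it.

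**1. Algebra.** Let G be arm, X a baseline covariate, and t = 0, 4, 8:

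Y(t) = m(t) + d(t)·G + b·X + e(t)

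Y(4) − Y(0) = [m(4) − m(0)] + [d(4) − d(0)]·G + [e(4) − e(0)]

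The term b·X is gone; the same holds for month 8. Group x Time consists of d(4) − d(0) and d(8) − d(0), so with complete data it is estimated from changes that do not contain X. If X has a slope b(t) that varies by visit, [b(4) − b(0)]·X remains and the arm contrast is adjusted for it.

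**2. Numerical check, complete data.** Fits used 166 per arm, visits at 0, 4 and 8 months, and four baseline covariates. Effects, covariances and slopes are assumptions.

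| Covariance | Covariates | Group x Time, month 4 / 8 | SE, month 4 / 8 | F |
|---|---|---|---|---|
| Compound symmetry | none | 0.10426 / 0.10631 | 0.11324 / 0.11324 | 0.57651 |
| Compound symmetry | main effects | 0.10426 / 0.10631 | 0.11324 / 0.11324 | 0.57651 |
| Unstructured | none | 0.10426 / 0.10631 | 0.1042 / 0.11877 | 0.61921 |
| Unstructured | main effects | 0.10426 / 0.10631 | 0.1042 / 0.11877 | 0.61921 |

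Under compound symmetry only the group main effect moved, from 0.050 (SE 0.144) to 0.128 (SE 0.115).

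**3. With covariate x time** (compound symmetry, complete data). When one covariate predicts change (assumed slope 0.3), the estimates move from 0.072 / 0.074 to 0.115 / 0.117 and the SE from 0.117 to 0.114. When none predicts change, they move from 0.104 / 0.106 to 0.115 / 0.117 and the SE goes from 0.113 to 0.114, so no precision is gained.

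**4. With dropout.** The plan gives no expected rate; the pilot's 3/12 = 25% (section 3) is assumed. Each row is 60 simulated trials under compound symmetry, with a true effect of 0.30 and covariates that predict level but not change.

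| Dropout | Mean month-8 estimate, none → main effects | RMS shift | SE |
|---|---|---|---|
| Unrelated to covariates | 0.299 → 0.300 | 0.12 SE | 0.1247 → 0.1238 |
| Related, equally in both arms | 0.291 → 0.291 | 0.13 SE | 0.1246 → 0.1237 |
| Related, opposite directions by arm | 0.238 → 0.285 | 0.40 SE | 0.1245 → 0.1238 |

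In the first two rows the SE falls by under 1%. In the third, main effects remove most of the bias. If in that last setting a covariate also predicts change (assumed slope 0.3), the month-8 means are 0.144 with no covariates, 0.210 with main effects and 0.280 with covariate x time.

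**5. Effect of an uncorrected imbalance.** A covariate just large enough to be flagged differs by 1.96 × sqrt(2/166) = 0.215 SD. If it correlates r with change, the unadjusted contrast is shifted by 0.215 × r: 0.04, 0.06 or 0.09 SD of change for r = 0.2, 0.3 or 0.4. Given that imbalance, the test statistic has mean 1.96 × r and variance 1 − r². The conditional false-positive rate is

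P(Z > (1.96 − 1.96r)/sqrt(1 − r²)) + P(Z < (−1.96 − 1.96r)/sqrt(1 − r²))

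- r = 0.2: P(Z > 1.600) + P(Z < −2.400) = 6.3%
- r = 0.3: P(Z > 1.438) + P(Z < −2.671) = 7.9%
- r = 0.4: P(Z > 1.283) + P(Z < −2.994) = 10.1%

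**6. Lost precision.** If covariates explain a share R² of the variance of change, the unadjusted SE is 1/sqrt(1 − R²) times the adjusted one: 1.026 at 5% and 1.118 at 20%. In participants, 332/(1 − R²) − 332 gives 17 and 83.

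**The case against.** The strongest objection is that main-effects-only entry is inferred. Section 4.f names a method and a list of covariates, and nothing in it excludes covariate-by-time terms. That stands: what is documented is a model that has not been written out. But main effects are the usual meaning of controlling for baseline factors in a standard analysis of covariance, and the stated test of improvement points to month 0 as a response. The omission therefore matters, because the default fit would not do what the section intends.

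The second objection also stands in part. Exact cancellation needs complete outcomes, and the plan keeps incomplete cases under a missing-at-random assumption. A reader might infer that the covariates do nothing at all. The documents do not support that: section 4.f foresees a check for differential dropout, and when dropout depends on a covariate differently by arm, main effects can shift the estimate materially.

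Two other stronger readings should be set aside. One is that every efficacy analysis is unadjusted. The Hypothesis 2a1 mediation analysis is a separate M-Plus analysis and not a Group x Time test, so this point does not reach it. The other is that the trial's error rate is inflated. Allocation is randomised, so over all randomisations the unadjusted test keeps its 5% level. The rates in step 5 apply only given one particular imbalance.

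Finally, the benefit depends on covariates predicting change and not merely level. The documents give no such correlation, so the gain may be small or nil.

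**Conclusion.** The point holds for the Group x Time tests of Aim 1 and Hypotheses 2a and 2b, on the reading that month 0 is a response and covariates enter as main effects. The stated adjustment and the imbalance rule then do not reach the tested term: exactly so with complete data, and nearly so when dropout is unrelated to the covariates or related to them equally in both arms.

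The randomised comparison remains valid. What is lost is correction of chance imbalance and some precision: conditional false-positive rates of about 6.3-10.1% for a covariate exactly at the flagging threshold with r of 0.2-0.4, and an SE 2.6-11.8% larger than needed at R² of 5-20%. Those correlations and R² values are assumptions. The cancellation does not depend on them. The section should be changed, because a better use of data already collected costs almost nothing.

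**What to change.** Write out the model in section 4.f, choosing one of two forms:

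- **(a)** Keep month 0 as a response and enter each prespecified baseline covariate with its covariate x visit interaction. Group x Time then remains the test and is adjusted.
- **(b)** Model months 4 and 8 as responses, with the baseline outcome and the covariates as adjusters, and replace the Group x Time test with adjusted group contrasts at month 4 and at month 8. The tested term must change with the model: Group x Time in a model of months 4 and 8 asks only whether the effect differs between those visits, and main-effect covariates cancel from it too.

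In either case, state the covariance structure, say that any variable added under the imbalance rule takes the same form, and describe as adjusted only the contrasts that these terms act on.

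The cost is a few lines of wording and no new data. With three visits, form (a) spends two interaction degrees of freedom per continuous covariate and 2 × (k − 1) for one with k categories. If the covariates do not predict change, form (a) brings little or no gain in precision and can raise the SE very slightly, as in step 3 (0.113 to 0.114).
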